5.4 Specimen Submission Criteria

- a. Patients must have specimens collected for submission as outlined in [Section 15.1](#).
- b. Patients must be offered the opportunity to participate in optional translational medicine studies as outlined in [Section 15.2](#).

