15.0 SPECIAL INSTRUCTIONS

15.1 Blood Serum Specimens (REQUIRED)

Specimens for translational medicine and banking (submitted to the Biospecimen Bank – Solid Tissue, Myeloma and Lymphoma Division, Lab #201) required for patient:

- a. Blood serum for HBV DNA, HBsAg, ultrasensitive HBsAg, anti-HBs, HBV RNA, HBV core-related antigen (HBcrAg) testing and serum cytokine analysis must be submitted at the following time points (see [Section 9.0](#)):
 1. At the time of registration (+/- 4 weeks)
 2. Every 8 weeks (+/- 2 weeks) from date of registration
 3. At time of HBV re-activation
- b. At each time point, 10 mL of blood will be drawn into red top tube(s) using institutional supplies, spun down at 1500 G for 10 minutes at room temperature, and serum aliquoted into 1 mL aliquots. Serum should be stored in a -70 to -80°C freezer (preferred, if available). Samples stored in a -70 to -80°C freezer may be batch shipped. If batch shipped, samples must be shipped within 3 months of collection.

If -70 to -80°C freezer is not available, then ship immediately on dry ice (ship overnight Monday – Thursday), or store in a -20°C to -80°C freezer and ship within 2 weeks, noting the storage temperature in the Specimen Tracking System.

Samples must be shipped (Monday – Thursday) on dry ice by overnight shipping for receipt Tuesday - Friday. Samples should not be shipped prior to a holiday. The SWOG Biospecimen bank is not able to receive frozen samples on Saturdays, Sundays, or holidays. See [Section 15.3](#) for specimen shipment instructions.

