15.2 Whole Blood Specimens (**OPTIONAL for Patient**)

- a. With patient's consent whole blood specimens for intracellular cytokine staining (ICC), ELISA, IFN-gamma elispot testing (submitted to the SWOG Biospecimen Bank – Solid Tissue, Myeloma, and Lymphoma Division, Lab #201) must be submitted at the following time points (see [Section 9.0](#)).
 1. At time of registration (+/- 4 weeks)
 2. 8-12 weeks from registration
 3. 24 weeks (+/- 4 weeks) from date of registration
 4. At time of HBV-re-activation
- b. At each time point, a total 50 mL of blood will be drawn into five to eight purple top (EDTA) tubes using institutional supplies. Blood should be shipped the day of collection, overnight at ambient temperature. Blood may be shipped on Monday through Friday for Tuesday through Saturday delivery. If shipping for Saturday delivery, please mark Saturday delivery and notify the Bank. See [Section 15.3](#) for specimen shipment instructions.

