HBV-specific T cell and B cell responses are weak in patients with chronic HBV infection. However, evidence from patients receiving immunosuppressive therapy confirms that there is ongoing immune control in chronic HBV infection. Multiple agents with different immunosuppressive and/or immunomodulatory properties have been associated with HBV-reactivation. Reactivation occurs with non-specific therapy like corticosteroids, as well as with targeted treatments like B cell-depleting agents and anti-TNF therapies. Therefore, perturbation of immune composition and/or specific antiviral pathways can result in reactivation. However, HBV reactivation does not occur in all patients who receive immunomodulatory therapies. We hypothesize that the composition, phenotype and function of immune cells at baseline will predict HBV reactivation after starting anti-cancer chemotherapy.

Aim 2 will conduct a case-control study comparing immune status in patients who develop HBV reactivation during chemotherapy with a 1:1 matched set of controls who were not on anti-HBV therapy and did not develop HBV reactivation. Specimens will be collected at the time points detailed in [Section 9.0](#) Study Calendar and [Section 15.0](#). Participants who are clinically diagnosed to have HBV reactivation will have an additional blood draw for future immune studies. All blood specimens will be collected from 444 study participants then shipped overnight to SWOG Biospecimen Bank for processing and storage in a -80°C freezer. Specimens will be sent from SWOG Biospecimen Bank to Drs. [name] and [name]'s laboratory at the Toronto Centre for Liver Disease for immune

studies detailed below. [name] and her immunology collaborators will have priority access to the specimens at SWOG Biospecimen Bank at all times.

The samples are the key novel aspect of the study. Using data from Translational Aim 1, we will identify patients with reactivation defined by increasing HBV viral load with an equal number of patients not experiencing HBV reactivation after treatment. The primary analysis will be performed on longitudinal samples comparing change from baseline upon starting chemotherapy in HBV reactivation patients and those without reactivation. Patients will be matched by age (5-year strata), sex, type of anti-cancer therapy (cytotoxic, immune or targeted) and chronic vs. past HBV.

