Serum analysis to identify serum biomarkers predicting HBV reactivation. We will use clinical assays to quantify HBV-specific antibodies in the serum and a comprehensive CBA or luminex assay to analyze immunological cytokines/chemokines in longitudinal serum samples. Arginase will be measured by ELISA. HBV RNA, HBcrAg and ultrasensitive HBsAg will be measured in the serum by qPCR (RNA) and ELISA (HBcrAg and ultrasensitive HBsAg) in patients who do and do not experience HBV reactivation to determine if the levels of these markers that indicated active transcription of HBV DNA in the liver increase prior to clinical reactivation and could be used as biomarkers of impending reactivation.

Understanding the serum profile of key molecules associated with HBV reactivation may provide a baseline predictor of HBV control during chemotherapy.

c. **Translational Aim 2. To identify demographic and clinical predictors and correlative immunologic biomarkers of HBV reactivation after receipt of anti-cancer therapy in patients with solid tumors and chronic or past HBV infection.**

The determinants of HBV reactivation in patients with solid tumors are not known. In this aim, we will identify the demographic and clinical predictors as well as immune correlates of HBV reactivation and hepatitis flare among all 444 study patients. For Aim 2, all immune studies will be performed on stored plasma and PBMCs that would have already been prospectively collected at predetermined time points as noted in [Section 9.0](#) Study Calendar and [Section 15.0](#) above. Immune tests will include ELISA, ICC assay, IFN-gamma elispot. If any immune test listed for Aim 2 has already been performed as part of the case control study in Aim 1, it will not be repeated in this aim. In the main clinical study, SWOG sites will collect clinical information for use in Aim 2. The following tests will be considered usual care monitoring for HBV patients receiving anti-cancer therapy and will be recorded at the study follow up time points listed in [Section 9.0](#) Study Calendar: ALT, total bilirubin, and INR. The primary outcome for Aim 2 is time to first evidence of HBV reactivation.

Statistical Analyses plan

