Only the patients randomized to the standard arm of each randomized study (chronic vs. past HBV infection) will be the potential participants for this aim. A case-control analysis, using a ratio of cases to controls of 1:1, will be conducted to explore baseline and changes of overall immune status and HBV-specific immune response factors that differ between patients with vs. without HBV reactivation. Based on expected rates of HBV reactivation for patients with chronic and past HBV infection (20%), we estimate that 22 patients with chronic and 22 patients with past HBV infection (n=44 total cases) will develop HBV reactivation. Under this scenario, we will also examine a matched set of 44 control patients. Matching will occur based on age and randomized study type (chronic vs. past HBV infection). Power is low in this setting and therefore this aim is considered exploratory, with any positive findings requiring validation in future studies. For a given binary predictor (i.e. immune status, group 1 = high vs. group 2 = low), 88 total patients (44 cases and 44 controls) is sufficient to detect an absolute difference of 26% in HBV reactivation rates (i.e. 7% for group 1 and 33% for group 2), assuming the overall rate of HBV reactivation is 20%, using a 2-arm binomial alpha=.05 test with 80% power. In addition, changes in overall immune status and HBV-specific immune responses after onset of cytotoxic chemotherapy or immunotherapy will be described for the cases and controls using descriptive statistics (means, standard deviations). To avoid incorrect inference induced by the potentially endogenous relationship between HBV reactivation and immune response, landmark analyses will be used, conditioning on patients surviving to a given assessment time without developing HBV reactivation.

The study will also assess the association of potential risk factors (including demographic, clinical, and immunologic markers) for HBV reactivation. For any potential demographic, clinical, or immunologic factor, time-to-HBV reactivation will be examined using Cox regression, adjusting for the stratification factors specified in the main clinical study. Analyses will be conducted for each randomized study (chronic vs. past HBV), each with a total sample size of n=222 patients. For instance, to identify a hazard ratio of 2.5 between patients with or without a given condition (say, status for a specified candidate marker or

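### Whole blood is optional, but the cell-based immune markers carry case numbers and power that hold only if every patient opts in

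*Combined protocol and SAP*

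**What the plan says.** **Whole blood is voluntary.** Section 15.2 is headed as optional for the patient and opens "With patient's consent whole blood specimens for intracellular cytokine staining (ICC), ELISA, IFN-gamma elispot testing". Section 5.4b makes only the offer compulsory: "Patients must be offered the opportunity to participate in optional translational medicine studies". Serum (Section 15.1) is required of everyone.

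**Cells come only from whole blood.** Section 18.2 has the bank obtain white cells from the EDTA tubes; the red-top tubes in 15.1 yield serum. The CyTOF, functional flow and ELISpot work in 18.1 needs cells, from 500,000 up to 5 million per assay. For Translational Aim 2, 18.1 says "all immune studies will be performed on stored plasma and PBMCs".

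**The counts assume everyone contributes.**
- Section 2.1 promises a repository of plasma and mononuclear cells from 444 patients.
- Appendix 18.1 says "All blood specimens will be collected from 444 study participants then shipped overnight to SWOG Biospecimen Bank".
- The case-control analysis takes 22 chronic and 22 past HBV cases from the standard arms, 44 in all, with 44 controls.
- The Cox analyses cover any demographic, clinical or immunologic factor: "Analyses will be conducted for each randomized study (chronic vs. past HBV), each with a total sample size of n=222 patients". The worked example gives 87% power at a hazard ratio of 2.5, and 18.1 concludes that power will usually suffice for hazard ratios of 2.5 or more.

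**The concern.** A marker measured on cells can be analysed only in patients who gave whole blood. Without an opt-in allowance, the number of usable cases, the pool of controls and the Cox sample are all stated at their ceiling. The plan does allow for loss elsewhere: Section 11.1 inflates the main sample for 10% dropout, and Section 11.2 assumes no information from those patients when it sizes the precision of the reactivation estimate.

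At stake is how the cell-marker results will be read. Someone who sees no association for a CyTOF or ELISpot marker would take 87% as the chance that a hazard ratio of 2.5 would have been found. The true figure depends on a participation rate that the plan never states.

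**Working it through.** **1. Inputs.** From 18.1: 20% reactivation; 111 + 111 = 222 standard-arm patients; n = 222 per cohort for Cox; hazard ratio 2.5; 40:60 split; stated power 87%. From Section 11: reactivation hazard 0.223 and death hazard 0.223 per year. From 7.8: 24 months of follow-up. Opt-in rate: not in the documents; 50% to 90% is my assumption.

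**2. The plan's case count.** 0.20 × 222 = 44.4, so the 44 cases are every reactivation expected in the two standard arms.

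**3. The plan's case-control size.** Two proportions, 7% vs 33%, two-sided 0.05, 80% power:
- n₀ = (1.96·√(2·0.2·0.8) + 0.842·√(0.07·0.93 + 0.33·0.67))² / 0.26² ≈ 36
- with the usual continuity correction, 44 per group, as stated.

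**4. The plan's Cox power.** Exponential model with competing death. Events in a group with n patients and hazard h:

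d = n · h/(h + 0.223) · (1 − exp(−2(h + 0.223)))

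- Higher-risk group: n = 133.2, h = 0.223, d₁ = 39.3
- Lower-risk group: n = 88.8, h = 0.223/2.5 = 0.0892, d₂ = 11.8
- Test statistic mean: ln 2.5 · √(d₁d₂/(d₁ + d₂)) = 0.916 × 3.011 = 2.759
- Power, one-sided 0.05: Φ(2.759 − 1.645) = 86.7%

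This model, with the first-named share of each split placed in the lower-risk group, reproduces all 16 cells of Table 18.1 within 0.8 points. The stated 87% therefore requires all 222 patients to contribute.

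**5. With an opt-in share f.** Events scale with f, so the test statistic mean is 2.759·√f, and cases with cells are 44·f.

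| Assumed opt-in | n per cohort | Cases with cells | Cox power, HR 2.5, 40:60 |
|---|---|---|---|
| 100% | 222 | 44 | 86.7% |
| 90% | 200 | 39.6 | 83.5% |
| 80% | 178 | 35.2 | 79.5% |
| 70% | 155 | 30.8 | 74.6% |
| 50% | 111 | 22.0 | 62.0% |

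**6. Where power falls below 80%.** f = ((1.645 + 0.842)/2.759)² ≈ 0.81. A two-sided Schoenfeld formula set to 87% at full n puts it at 0.82.

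**7. Case-control difference.** With the formula of step 3 and the plan's mean rate of 20%, the detectable difference is 26 points at 44 per group, about 29 at 35, about 31 at 31, and about 37 at 22.

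**The case against.** Much of the case on the other side stands.

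- **No figure is miscalculated for its own n.** The 44 cases, the 44 per group and the 87% all reproduce. What is missing is an allowance, and the 444 wording contradicts 15.2.
- **Most of what the n = 222 sentence covers is unaffected.** Demographic and clinical factors need no whole blood. Antibodies, serum cytokines, HBV RNA, core-related antigen and ultrasensitive HBsAg come from required serum. The 87% is given as an example for a generic marker. But the same text names immunologic factors without distinction, and its closing statement on adequacy makes no exception for cells.
- **The case-control part is already described as low-powered and exploratory, needing validation.** That softens the point there. It does not extend to the Cox part, and an exploratory analysis still needs a realistic count of usable cases.
- **The loss may be small.** At 90% opt-in it is 3 to 4 points.

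A reader might also infer more than the documents support. No power figure uses 444, which is only the described scope of collection. The expected number of reactivations does not fall with opt-in; only the number with cells does. Nothing shows that consenting patients differ from the rest, so selection is a possibility and not a finding. Rescaling 87% as a two-sided figure does not fit the model behind Table 18.1: two-sided, that model gives 78.8% at full n. The text's two-sided label is a separate matter.

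**Conclusion.** The point holds for cell-based markers only. Sections 5.4b and 15.2 make their source material optional, while Section 2.1 and Appendix 18.1 treat it as collected from everyone, and nothing in the documents reconciles the two. The 44 cases, n = 222 and 87% are upper limits for these markers, reached only at 100% opt-in.

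The size of the shortfall rests on an opt-in rate that the documents do not give and on opt-in being unrelated to outcome or marker status. Across 90% to 50%, usable cases run from about 40 to 22 and power at a hazard ratio of 2.5 from about 83% to 62%. The co-primary and secondary clinical analyses are untouched.

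**What to change.** - In Appendix 18.1, list which markers use required serum (full n) and which use whole blood (opt-in subset).
- For the whole-blood markers, state an opt-in range and restate expected cases, available controls and power over it; the table above can serve as a model.
- Limit the statement that power suffices for hazard ratios of 2.5 or more to markers with full n.
- In Sections 2.1 and 18.1, replace 444 for mononuclear cells, plasma and blood specimens in general with wording that depends on consent. The 444 for required serum can stay.

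This changes wording and a few figures, and nothing in trial conduct. The cost is less favourable stated power for the cell markers.

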18.2 Instructions for the SWOG Biospecimen Bank

NOTE: The SWOG Biospecimen Bank will prepare specimens for immune studies by separating the plasma, isolating the peripheral blood mononuclear cells (PBMCs), and then cryopreserving

1. Frozen serum

Processed, frozen serum aliquots will be received at up to 7 time points. Upon receipt, the Bank will accession and barcode before banking in a -80°C freezer until distribution for testing.

At the end of the study, the Bank will receive notification from the SWOG Statistics and Data Management Center with the cases to distribute for HBV DNA, HBsAg, anti-HBs, HBV RNA, HBV core-related antigen testing, and serum cytokine analysis.

2. Blood in EDTA tubes

Fresh whole blood collected in EDTA tubes will arrive at ambient temperature from up to 7 time points per patient. At each time point, the Bank will accession and process all specimens for white blood cells (WBC) using a red blood cell lysing technique. WBCs will be aliquoted with freezing media in vials with 1×10^7 cells per vial. WBCs will be stored in a liquid nitrogen vapor phase freezer until distribution for future testing.

At the end of the study, the Bank will receive notification from the SWOG Statistics and Data Management Center with the cases to distribute for ICC, ELISA, IFNg, and ELIspot testing.

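### Section 18.2 gives two incompatible preparations for EDTA blood, and its numbered step does not yield the stored plasma and PBMCs that Translational Aim 2 specifies

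*Combined protocol and SAP*

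**What the plan says.** Section 18.2 opens with a note that the Bank will "prepare specimens for immune studies by separating the plasma, isolating the peripheral blood mononuclear cells (PBMCs), and then cryopreserving". Item 2 of the same section, on EDTA tubes, tells the Bank to "process all specimens for white blood cells (WBC) using a red blood cell lysing technique". The cells go into vials of 10 million with freezing medium, and "WBCs will be stored in a liquid nitrogen vapor phase freezer until distribution for future testing". Item 2 mentions neither PBMC isolation nor a plasma aliquot. At the end of the study the Bank is to be notified of "the cases to distribute for ICC, ELISA, IFNg, and ELIspot testing".

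Section 18.1c, Translational Aim 2, says that "all immune studies will be performed on stored plasma and PBMCs that would have already been prospectively collected", and gives the immune tests as ELISA, ICC and IFN-gamma ELISpot. Section 2.1 describes the planned repository as plasma and PBMCs from 444 patients.

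On storage, Section 18.1b sends all blood specimens to the Bank "for processing and storage in a -80°C freezer". On timing, Section 15.2 lists four whole blood draws, while Section 18.2 item 2 expects EDTA blood from as many as seven. (Aim numbers here follow the subheadings of Section 18.1.)

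**The concern.** A note and a numbered step in one instruction describe different products, and the numbered step is the one that bench staff are likely to carry out. The Aim 2 text and the repository description agree with the note, so item 2 stands alone.

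The mismatch is more than untidy wording, because processing cannot be undone. A baseline sample cannot be redrawn once anti-cancer therapy is under way, and Section 18.1b hypothesizes that immune cells at baseline predict reactivation. Under Section 18.2 the EDTA product is released for testing only at the end of the study, so a wrong preparation might not be noticed before then.

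There is also an analytic side. Suppose the practice changes partway through, with some samples prepared under the note and others under item 2. Marker values could then differ by preparation. Neither description of the case-control matching in Section 18.1 includes sample handling.

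**Working it through.** The plan gives no figure to reproduce on this point. The check is a comparison of texts, with one side calculation.

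**1. The texts side by side**

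| Place | Product from EDTA blood |
|---|---|
| Section 18.2, note | plasma, plus isolated and cryopreserved PBMCs |
| Section 18.2, item 2 | total white cells after red cell lysis; nothing else named |
| Section 18.1c (Aim 2) | stored plasma and PBMCs |
| Section 2.1 | repository of plasma and PBMCs |
| Section 18.1b (Aim 1 assays) | leukocytes, lymphocytes, myeloid cells; PBMCs not named |

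Item 2 taken alone yields neither of the two products named for Aim 2.

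**2. Is there another source of plasma?** Section 15.1 collects red-top tubes and aliquots serum. EDTA blood (Section 15.2) is therefore the only stated source of plasma. Item 2 sends the EDTA product for ELISA, among other tests, but stores only cells.

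**3. Which work is exposed?** The cell and plasma assays are: ICC, ELISpot and any plasma ELISA. The following are not:
- HBV-specific antibodies, cytokines and chemokines, HBV RNA, HBcrAg and ultrasensitive HBsAg, which Section 18.1b measures in serum, with the arginase ELISA listed in the same paragraph;
- demographic and clinical predictors of reactivation, which need no EDTA blood;
- the primary and secondary endpoints and the sample size.

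**4. Cell numbers.** Section 18.1b gives the needs of the three Aim 1 assays as 0.5 million, 1 to 2 million and 3 to 5 million cells.

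- Low: 0.5 + 1 + 3 = 4.5 million
- High: 0.5 + 2 + 5 = 7.5 million
- Vial size (Section 18.2): 10 million white cells

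If the stated needs mean mononuclear cells (an assumption), the mononuclear share required of the vial contents is need ÷ (vials × 10 million):

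- one vial: 4.5/10 = 45% to 7.5/10 = 75%
- two vials: 4.5/20 = 22.5% to 7.5/20 = 37.5%

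The documents give neither the mononuclear share nor the number of vials from a 50 mL draw. This demonstrates neither a shortage nor sufficiency.

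**5. How many patients?** Section 18.1 expects 22 cases per cohort, so 2 × 22 = 44 cases, with 44 controls, 88 in all. Whole blood is optional for the patient (Section 15.2), so the number exposed is the consenting subset, whose size the documents do not give.

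**6. Time points.** Section 15.2 lists registration, 8 to 12 weeks, 24 weeks and reactivation, which is 4. Section 18.2 item 2 allows up to 7, so 3 are unaccounted for.

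**The case against.** The strongest reply is that nothing has been shown to be lost. Total white cells still include the mononuclear cells. The Aim 1 text speaks of leukocytes in general and isolates B cells later by magnetic selection. The stated cell needs are smaller than one vial. The note belongs to the same instructions as item 2, so plasma could be drawn off under the note before lysis; item 2 omits that step but does not forbid it. On storage, the -80°C sentence in Section 18.1b is general, while Section 18.2 gives the rule by specimen type. The plan itself calls the case-control work exploratory and low in power.

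Most of this stands, and it sets the limits of the point. A reader might infer that samples prepared under item 2 would not supply the planned assays. The documents do not support that: nowhere do they say that lysed, cryopreserved white cells are unsuitable for ICC, ELISpot or CyTOF. A reader might also infer that translational objectives 1.3a and 1.3b could not be answered, or that all 88 cases and controls depend on these samples. Neither follows, given the separate serum stream, the clinical predictors in 1.3b and the optional whole blood draw. Nor do the documents settle which preparation is intended, so it cannot be assumed that the note is right and item 2 wrong.

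The reply does not remove the contradiction itself. Combining the note with item 2 might rescue the plasma. It does not reconcile PBMC isolation with vials of total white cells.

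**Conclusion.** Wrong as written: an internal inconsistency, limited to the translational aims. Section 18.2 prescribes two different preparations of the same tubes, and its operative step does not deliver the material on which Section 18.1c rests all Aim 2 immune studies and which Section 2.1 promises for the repository. The cell and plasma assays in consenting patients are at risk. How far they would be compromised cannot be sized from the documents, because the suitability of lysed cells, the mononuclear share and the vials per draw are not given.

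The conclusion assumes that the Bank works from item 2 as printed and that no separate laboratory manual overrides it. The storage and time-point conflicts are minor but should be settled in the same edit.

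**What to change.** First, have the immune laboratory confirm which product its assays need. Then bring the Section 18.2 note, Section 18.2 item 2 and the Section 18.1 text into agreement on:
- one preparation, stating whether plasma is aliquoted before the cells are processed;
- one storage condition for each specimen type;
- one count of EDTA time points, consistent with Section 15.2.

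Record for every EDTA sample already banked how it was processed and stored. If more than one method was used, the translational analysis should take the method into account, for example as a matching factor or covariate, or in a sensitivity analysis restricted to one preparation.

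The cost is a change to the Bank instructions and possibly some extra bench time per sample. The main trial's design, sample size and analysis do not change.
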